Aim 3. Determine whether iCanQuit is significantly more cost-effective than QuitGuide, as measured by cost per additional quitter, incremental cost-effectiveness ratio (ICER), and incremental cost per quality-adjusted life year (QALY). Importance of

this aim: will provide payers (e.g., insurance companies) and policymakers results needed to decide whether to adopt iCanQuit.

[figure not shown]
Exploratory Aim: Explore whether iCanQuit, as compared to QuitGuide, has higher quit rates for those with these baseline factors: (a) low acceptance of sensations, emotions, and thoughts that cue smoking, (b) heavy smoking (≥ 20 cigarettes/day), (c) current mental health symptoms, and (d) being racial/ethnic minority. Importance of this aim: will potentially identify key subgroups that benefit most from iCanQuit, and thereby aid in reducing tobacco-related health disparities.

Innovations. (1) ACT's innovative features augment the US Clinical Practice Guidelines; (2) ACT follows an innovative theory: Relational Frame Theory; (3) ACT on the smartphone is novel; (4) First randomized trial of a smartphone app for adult smoking cessation; (5) The first time that the following have been tested for **any** behavior outcome: (a) ACT delivered via smartphone, (b) mediation of the effects of a smartphone app, (c) cost-effectiveness of a smartphone app, and (d) exploration of subgroups who benefit most from a smartphone app. While there are thousands of apps and hundreds for smoking [2], testing an app's efficacy is scientifically innovative. That's a critical gap this application fills.

Approach

Randomized trial experimental design. We will conduct a fully-powered two-arm randomized controlled trial that compares iCanQuit to QuitGuide, which follows the USCPG. To balance baseline variables between the two conditions, we will stratify randomization by daily smoking frequency (≤ 20 vs. ≥ 21), education (\leq high school vs. \geq some college), race/ethnicity (minority race/ethnicity vs. non-Hispanic White) and depression screen (CES-D score ≤ 15 vs. ≥ 16). Moderators will be measured at baseline. Mediators will be measured at baseline and three months post randomization. Consistent with cessation trial designs [60], cessation and cost-effectiveness outcomes will be measured at 3, 6, and 12 months post randomization.

Figure 1. Experimental Design

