Exploratory aim: Moderators of treatment outcome. Hypothesized moderators of treatment effectiveness will be heaviness of smoking (smoking at least 20 cigarettes per day vs. less than 20 at baseline), acceptance of cravings to smoke (AIS scores below vs. above the median), mental health symptoms (positive vs. negative screen for depression, anxiety, or heavy alcohol use), and racial/ethnic minority status (Caucasian vs. minority). Mental health symptoms will be assessed as follows: (1) depression screening via the 10-item Center for Epidemiologic Studies Depression Scale (CES-D; cutoff ≥ 10) [83, 84]; (2) anxiety screening via the Generalized Anxiety Disorder Scale; (GAD-7; cutoff ≥ 10 , [85]); (3) alcohol screening via the Alcohol Use Disorders Identification Test—Consumption items (AUDIT-C; cutoffs ≥ 4 drinks/day for women, ≥ 5 drinks/day for men or 7 drinks/week for women, 14 drinks/week for men [86, 87]).

Treatment acceptability/adherence: Treatment satisfaction and utilization. Measured with the 8-item Treatment Satisfaction/Utilization Scale used in our pilot. Sample satisfaction item: "Overall, how satisfied are you with your assigned app?" Sample utilization items: "Overall, about how many times per week did you use the strategies taught in your assigned app?" and "How useful was your assigned app's quit plan?"

Cessation pharmacotherapy usage: Measures number of days per week, number of total weeks, and start/end dates, that participants on their own elected to use (1) nicotine replacement therapy (i.e., patch, gum, lozenge, inhaler, nasal spray), (2)

varenicline, (3) bupropion, and (4) other (fill in).

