Analyses. Aim 1. Our primary outcome hypothesis is that iCanQuit will have significantly higher 30-day point prevalence abstinence at 12 months post-randomization than QuitGuide. **Analyses:** For each comparison of the arms on the primary and all secondary endpoints, we will use a logistic regression model with complete case smoking cessation outcome [9-14]. The model will adjust for all stratification factors as well as baseline factors that might be imbalanced after randomization. In addition, we will conduct these analyses: (1) multiple imputation of missing outcomes [90-92], (2) missing equals smoking outcomes [9-14], (3) using a secondary cessation outcome of no use of cigarettes **and** other nicotine or tobacco products except FDA-approved nicotine replacement therapies. Finally, we will compare the two arms on utilization of their assigned app.

Aim 2. We hypothesize that the iCanQuit arm's (but not the QuitGuide arm's) smoking cessation outcomes will be strongly mediated by these psychological measures that are central to the theoretical model underlying ACT: commitment to quitting and acceptance of internal (a) sensations, (b) emotions, and (c) thoughts that cue smoking. This hypothesis is consistent the ACT model and prior ACT for smoking cessation intervention studies [16, 17, 20, 82]. **Analyses:** For each mediator, the model is expressed as three regression equations that relate the main independent variable X

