(ACT intervention), the mediator M (change from baseline to 3-months post randomization in the acceptance variable, and/or commitment to quitting smoking despite internal cues), and the binary endpoint Y at 12-months post-randomization (e.g., 30-day abstinence). The first regression describes the total intervention effect (X) on the outcome (Y): $\text{logit}(Y) = \gamma_1 + \tau X$, where the parameter τ measures the total intervention effect. The second regression describes the impact of the intervention (X) on the mediator (M): $M = \gamma_2 + \alpha X$. The third regression describes the simultaneous impacts of the intervention (X) and mediator (M) on the outcome (Y): $\text{logit}(Y) = \gamma_3 + \tau'X + \beta M$. Since the endpoint is binary, the mediation effect is the product term $\alpha\beta$, whose empirical distribution will be estimated via 5000 bootstrapped samples. Bootstrapping is a resampling method which provides a powerful test of mediation that does not rely on normality assumptions [93-95]. Randomization should remove potential confounding effects [92, 93], and if needed, we will adjust each model by covariates that differ at baseline or predict outcome. Following VanderWeele and Preacher methods [94, 95], we will also explore any interactions between mediators and treatment arm. And we will explore whether utilization of assigned app and usage of cessation pharmacotherapy mediates cessation outcomes.

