
Exploratory Aim. This aim will explore whether iCanQuit, as compared to QuitGuide, has higher quit rates for those with these baseline factors: (a) those scoring low on acceptance of sensations, emotions, and thoughts that cue smoking, (b) heavy smokers (≥ 20 cigarettes/day), (c) smokers screening positive for mental health symptoms, and (d) being a racial/ethnic minority. **Analyses:** This aim will explore key moderators of ACT treatment outcomes and aid in the critical effort to improve quit rates for these high-risk groups [101-105]. The ACT model suggests that, in addition to being a key mechanism (i.e., mediator) of treatment, baseline acceptance is a moderator of treatment outcome [22]. Specifically, we hypothesize that people who avoid their

triggers to smoke (i.e., low acceptance) will benefit most from ACT because ACT teaches skills to overcome avoidance. We also hypothesize that this focus on acceptance may be especially helpful for heavy smokers and those with mental health symptoms because physical, emotional, and cognitive cues to smoke are stronger for these individuals [106-109]. Finally, testing moderation by race/ethnicity will allow us to generate hypotheses about whether minorities overall respond differently to ACT than non-Hispanic Caucasians. We will explore moderation with separate logistic regression models for each moderator variable, where 30-day abstinence at 12-months post randomization is the outcome (Y). The model will include the moderator (Z), group assignment (X), and an interaction between moderator and group assignment (X*Z). Statistically significant interactions will be assessed with plots showing how the slope of Y on X is dependent on the value of Z. The slopes will be derived from logistic regressions that correspond to the prediction of Y from X at a single value of moderator Z.

Power. We determined sample size with 5,000 iterative simulations aimed at 80% power for Primary Aim 1. We used the following parameters: (1) participants randomized to one of the two arms; (2) two-sided test with $\alpha = .05$; (3) intent-to-treat analysis where, as standard in smoking cessation trials, all those with missing data are coded as smokers [11, 60]. The calculations do not account for potentially higher effect sizes from the adjustment of stratification factors.

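### Only the Aim 1 model fixes the randomization strata as covariates: the moderator models omit them and the mediation equations leave them optional, which costs little for moderation but can bias the mediated effect.

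*Combined protocol and SAP*

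**What the plan says.** Under Randomized trial experimental design, the plan will "stratify randomization by daily smoking frequency (≤ 20 vs. ≥ 21" cigarettes a day, and also by education, race/ethnicity and a CES-D depression screen (15 or below vs 16 or above).

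Under Analyses, Aim 1, the covariate rule is explicit: "The model will adjust for all stratification factors as well as baseline factors that might be imbalanced after randomization". Its scope is the arm comparisons: "For each comparison of the arms on the primary and all secondary endpoints, we will use a logistic regression model".

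Under Analyses, Exploratory Aim, the rule is a closed list: "The model will include the moderator (Z), group assignment (X), and an interaction between moderator and group assignment (X*Z". Nothing else in that section adds covariates.

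Under Analyses, Aim 2, the total-effect, mediator and outcome equations are written with arm and mediator only. The text relies on randomization to deal with confounding, then adds: "if needed, we will adjust each model by covariates that differ at baseline or predict outcome". The strata are not named there, and no criterion for need is given.

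The Power section says its calculations leave out any benefit from adjusting for the strata. It also says the target was raised from 1622 to 2500 for the Exploratory Aim analyses.

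**The concern.** The plan sees value in adjusting for the strata and makes it a rule for Aim 1, but does not carry it into two other sets of models. Two things are at stake.

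- **Moderation.** If the strata predict quitting, leaving them out of a logistic model pulls the odds ratios slightly toward 1 and gives up a little power. The subgroup odds ratios are then conditional on fewer covariates than the Aim 1 odds ratio. The plan recruits 2500 - 1622 = 878 extra participants for these models, so it is odd to forgo precision that costs nothing.
- **Mediation.** The arm is randomized, so its effects on the mediator and on quitting are protected. The mediator (change in acceptance or commitment from baseline to three months) is not randomized. If depression or smoking level, say, affects both that change and later quitting, the coefficient β is confounded, and so is the tested product αβ. The Power section labels this Primary Aim 2, so it is not merely exploratory.

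**Working it through.** **1. The plan's own figure.** Inputs from Power: 11% vs 7%, two-sided 0.05, 80% power.

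n per arm = [1.960·√(2·0.09·0.91) + 0.8416·√(0.11·0.89 + 0.07·0.93)]² / 0.04² = (0.7932 + 0.3398)² / 0.0016 ≈ 803, or 1606 in total. The stated 1622 comes from simulation and is about 1% higher; at 811 per arm the formula gives 80.4% power. At 1250 per arm, unadjusted Aim 1 power is 93.8%. The sample size therefore reproduces and does not depend on this point. The plan states no power for the interactions.

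**2. Moderator models with and without strata.** From the documents: quit rates 7% and 11%, N = 2500, and 0.84 × 2500 = 2100 complete cases (84% retention, Follow-up survey methods). Assumed, because the documents give no values: stratum prevalences 30/40/30/50%; each stratum's odds ratio for quitting 0.8, 0.67 or 0.5; true interaction odds ratio 2.0; and, for a moderator that is not a stratum, a 50% split unrelated to the strata. Method: large-sample logistic regression with sandwich standard errors.

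| Moderator | N | Power without → with strata, odds ratio 0.8 | 0.67 | 0.5 |
|---|---|---|---|---|
| Not a stratum | 2500 | 66.6 → 66.8% | 65.8 → 66.3% | 63.3 → 64.1% |
| Not a stratum | 2100 | 59.0 → 59.2% | 58.3 → 58.8% | 55.8 → 56.7% |
| Is a stratum | 2500 | 59.5 → 59.7% | 56.4 → 56.8% | 50.6 → 51.2% |

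The gain is 0.1 to 0.9 points. The unadjusted interaction odds ratio is 1.97 to 2.00, against 2.00 adjusted. The overall treatment odds ratio moves from (0.11/0.89)/(0.07/0.93) = 1.642 to between 1.645 and 1.668, a shift under 2%.

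A second simulation used stronger assumptions: quit rates of 10-12%, N = 2500, a moderator related to depression, and four strata each with an odds ratio of 1.5, 2.0 or 2.5. Power rose from about 71% to 72, 73 and 75%. The unadjusted interaction log odds ratio was 0.65 to 0.69, against 0.69 to 0.70 adjusted. So about 4 points is the upper end.

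**3. Mediation.** α is unchanged in expectation, because arm is independent of the strata; any bias in αβ comes through β. Assumed: overall quit rate 9% (the mean of 7% and 11%), α = 0.3 SD, β = 0.5 per SD on the log-odds scale, residual arm effect 0.3 on the log-odds scale, prevalences as above, and each stratum lowering both the mediator (by 0.1 to 0.3 SD) and quitting (odds ratio 0.8 to 0.5). Fitting the outcome equation without strata gives:

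- weakest case (0.8, 0.1 SD): β = 0.517, αβ = 0.3 × 0.517 = 0.155 against 0.150, or +3%;
- middle case (0.67, 0.2 SD): β = 0.559, αβ = 0.168, or +12%;
- strongest case (0.5, 0.3 SD): β = 0.636, αβ = 0.191, or +27%.

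With the strata included, β returns to 0.500. If the strata move mediator and quitting in opposite directions, the omission makes αβ too small instead.

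**The case against.** **The mediation text already allows adjustment.** Its clause covers each model and admits covariates that predict outcome, which is the case that matters. This stands in part: the strata are not pre-specified, rather than excluded. But the clause gives no criterion and leaves the choice until data are seen. Its other trigger, a baseline difference, is the one stratified randomization makes unlikely for these factors.

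**The moderator analyses are exploratory and the loss is tiny.** This stands. No document supplies a stratum effect, and a model with only the three terms is a legitimate choice for generating hypotheses.

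**Some moderators already carry a stratum.** This stands too. Race/ethnicity is a stratum and also a moderator: "racial/ethnic minority status (Caucasian vs. minority". Heavy smoking (20 or more) differs from its stratum (21 or more) only for people reporting exactly 20 a day. The mental-health moderator includes a depression screen that overlaps the CES-D stratum. A rule to add all strata to every model would enter race/ethnicity twice.

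A reader might infer more than the documents support:

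- *That the subgroup odds ratios cannot be compared with Aim 1.* Non-collapsibility is a difference in estimand, and the computed shift at the planned quit rates is under 2%.
- *That imbalance of strata between arms within the low-acceptance or mental-health groups is a bias.* Within a baseline-defined subgroup it is chance imbalance, which the standard errors already reflect.
- *That the main effect of the moderator is distorted.* The plan interprets the interaction and the arm effect at each moderator level, not that main effect.
- *That Aim 2 claims 60% mediation of a different effect from the one Aim 1 reports.* The 60% (acceptance) and 25% (commitment) are planning assumptions in Power, and the tested quantity is αβ.

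**Conclusion.** The point holds in two parts of unequal weight. For the moderator models it is a minor inconsistency: about 0 to 1 point of interaction power at the planned quit rates, and up to about 4 points under stronger assumptions. Including the strata is still worthwhile, because it is free and puts the subgroup odds ratios on the same covariate footing as Aim 1. For mediation it is a pre-specification gap with a possible bias behind it. Randomization does not remove confounding of the mediator-to-outcome path, and omitting strata that predict both mediator and quitting would inflate αβ by about 3% to 27% if they act in the same direction.

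Every size here rests on assumed stratum effects and prevalences. If the strata do not predict quitting, both costs vanish. Adjusting for them removes only the confounding they carry; other mediator-outcome confounders would remain. The primary Aim 1 analysis and its sample size are unaffected.

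**What to change.** - **Analyses, Exploratory Aim.** Add: *Each moderator model will also include the randomization stratification factors, except a factor that is itself, or is nearly identical to, the moderator.* To leave no later judgement, name the exceptions: the race/ethnicity stratum in the race/ethnicity model and the smoking stratum in the heavy-smoking model.
- **Analyses, Aim 2.** State that the stratification factors enter all three equations as a fixed rule, and keep the existing clause for further covariates. Limit the sentence on randomization and confounding to the effects of arm on mediator and on outcome.

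If unadjusted models are preferred, give the reason. The cost is one sentence for each covariate rule and one reworded sentence. All four factors are collected before randomization, so no new data and no change to the sample size are needed.

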We also considered pharmacotherapy comparisons. But many participants would be ineligible for use (e.g., medical condition) and, if disseminated, many people would face access barriers (e.g., medication affordability). Some medications (e.g., varenicline) require a physician visit and prescription. For Nicotine Replacement Therapy (NRT), adequately addressing side effects for a nationally-recruited sample who will have had no prior personal contact with the study would be problematic [74, 75].

Table 4. Participant surveys and time points when they will be administered. (All participants)

Measure	Screening	Baseline	3- month	6- month	12- month	Purpose
Eligibility & Enrollment (24 items)	x					Eligibility, Enrollment, & Stratification
Demographics (19 items)		x				Stratification & Exploratory
Nicotine Dependence (6 items)		x	x	x	x	Stratification & Aim 1
Smoking/Tobacco History (4 items)		x				Exploratory Aim
Tobacco Use (6 items)		x	x	x	x	Aim 1

Acceptance of cues (27 items)	x	x			Aim 2 & Exploratory
Quality of Life (8 items)	x	x			Exploratory Aim
Quality of Life (6 items)			x	x	Exploratory Aim
Panic Symptoms (5 items)	x	x	x	x	Exploratory Aim
PTSD Symptoms (6 items)	x	x	x	x	Exploratory Aim
Generalized Anxiety Symptoms (7 items)	x	x	x	x	Exploratory Aim
Social Anxiety Symptoms (17 items)	x	x	x	x	Exploratory Aim
Depression Symptoms (20 items)	x	x	x	x	Exploratory Aim
Distress Tolerance (6 items)	x	x			Exploratory Aim
Values (10 items)	x	x			Aim 2
Growth Mindset (6 items)	x	x			Exploratory Aim
Quitting Self-Efficacy (1 item)	x				Stratification
Alcohol Use (4 items)	x	x	x	x	Exploratory Aim
Mobile Device Use (8 items)	x				Exploratory Aim
Receptivity/utilization (14 items)		x			Acceptance/Adherence
Receptivity/utilization (2 items)			x	x	Acceptance/Adherence
Cessation & Extra Aids (5 items)		x	x	x	Aim 1 and Exploratory
Willingness to discuss (1 item)				x	Follow-up

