Follow-up survey methods. For trial integrity, the follow-up data will be collected by our survey research unit that will be (1) blind to random assignment and (2) collecting cessation outcome data outside of the intervention apps. At each follow-up, we will send reminder letters. Each follow-up survey and Internet tracking will collect address information. The **online-telephone-mailed sequence** data collection protocol is as follows: 1) Three email attempts to complete the online version of the survey; 2) Eight attempts to complete a **telephone** version of survey (one call per day from a trained surveyor); 3) Send a paper version of the survey via **US mail**. Based on our ACT smartphone pilot RCT experience, we conservatively estimate this protocol will yield 84% retention. And to further boost retention, we will make the following protocol enhancements at all follow-up points: (1) mail a \$2 pre-incentive letter (noncontingent incentives increase retention [88]) 2 weeks before the first online survey invitation (i.e., Day -14); (2) provide a \$10 incentive for completing the online survey within 24 hours [89]; and (3) send a postcard with two questions about smoking status.

Table 5. Schedule of key activities.

Year of study	1				2				3				4				5				06 NCE			
Quarter	Q1	Q2	Q3	Q4	Q1	Q2	Q3	Q4	Q1	Q2	Q3	Q4	Q1	Q2	Q3	Q4	Q1	Q2	Q3	Q4	Q1	Q2	Q3	Q4
1. Refinement & Usability	xxx	xxx	xxx	xxx	xxx	xxx																		
2. Set up ^a	xxx	xxx			xxx	xxx	xxx																	
3. Recruitment							xxx	xxx	xxx	xxx	xxx	xxx	xxx	xxx	xx									
4. Interventions							xxx	xxx	xxx	xxx	xxx	xxx	xxx	xxx	xxx	xxx	xxx	xxx	xxx					
5. Outcome Surveys ^b								xx	xxx	xxx	xxx	xxx	xxx	xxx	xxx	xxx	xxx	xxx	xxx	xxx				
6. Data Entry & QC ^c								xxx	xxx	xxx	xxx	xxx	xxx	xxx	xxx	xxx	xxx	xxx	xxx	xxx	xx			
7. Analyses								xxx	xxx	xxx	xxx	xxx	xxx	xxx	xxx	xxx	xxx	xxx	xxx	xxx	xxx	xxx	xxx	xxx
8. Dissemination																						xxx	xxx	xxx

^a Set up study procedures, survey instruments, recruitment materials and advertising; IRB application. ^b3,6,&12 month outcome survey administration protocol (29 days long) timed to participant randomization date. ^cTelephone & mailed versions of each survey are data entered by a trained surveyor. A 20% random sample of entries are checked against audio-recorded telephone surveys and mailed hard copies. Errors over 1% trigger 100% batch re-entry and surveyor performance remediation.

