Telephone administration of the surveys will be conducted by trained staff. If the staff member gets voicemail, a short and simple message will be given letting the participant know the purpose of the call and encouraging him/her to call the study's toll-free number. Mailed surveys will include a letter inviting participants to complete the survey, a printed survey form, a self-addressed-stamped-return-envelope for the completed survey.

Potential risks to participants

The main risk to participation in this study is a small risk of breach of confidentiality. A breach could possibly occur if, for example, an unauthorized person accesses the study's database records and/or hard copy records, telephone survey conversations are accidentally overheard by someone who does not know the participant smokes or is taking part in a smoking cessation study. Also, some participants might feel emotional upset during their assigned intervention or embarrassment when talking about their smoking during the telephone surveys. Finally, some smokers making quit attempts may experience some short-term discomfort associated with nicotine withdrawal. Participants will be fully apprised of all anticipated risks in the informed consent and other intervention materials.

Protection against risk

All research activities will be reviewed and approved by the IRB at Fred Hutch to ensure that participants are adequately protected against risk. The research aims and activities, as well as risks and benefits, will be explained in detail to all potential participants prior to obtaining informed consent. Steps to protect against risk are described below:

Protection against breach of confidentiality: How survey data are processed and stored in HIPAA compliant server

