Several procedures will be used to maintain data integrity. All databases will be stored in a centralized location at Fred Hutch on a secure server. Data will be backed up daily and access will be password protected and limited to persons working on the

project. Persons will only have access to specific data required for their project tasks. Identifying information will be stored separately from the assessment data. Data will be audited on an ongoing basis to ensure confidentiality safeguards are being maintained and data integrity is being maintained. Data entry systems will be set-up to allow field checks, range checks for continuous variables, valid value checks for categorical variables, and checks for logical consistency of responses. Queries and data reports will be generated on a routine basis to monitor data quality.

Guidelines for Monitoring and Reporting Unexpected and Adverse Events

Monitoring

Throughout the study, the Principal Investigator, Co-Investigator, and Project Manager will monitor participants for adverse events and protocol compliance. The project manager will complete monthly reports on participant progress and status, any adverse events, and any protocol deviations. Protocol adherence will be monitored by the Principal Investigator.

Reporting

Study staff will be trained, and required, to report all unexpected and adverse events to the Principal Investigator. Adverse events beyond what would be expected in the course of smoking cessation will be reported to the Fred Hutch's IRB in accordance with Fred Hutch policy.

Definitions

In general, unexpected events (UEs) include any event, adverse or otherwise, that was not described as part of the study risks. For this trial, an example of an unexpected event that is not adverse is a participant who has become very unhappy with trial procedures. Adverse events (AEs) are any untoward occurrence with a trial participant whether or not it can be considered to be related to their smoking cessation. An example of an adverse event in this trial could include an increase in depressive symptoms. Serious adverse events (SAEs) include any AE that results in death, a real risk of dying, inpatient hospitalization, persistent or significant disability/incapacity, or AEs that require intervention to prevent permanent impairment or damage. In this trial, an example of a serious adverse event would be a suicide attempt.

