UEs, AEs, and SAEs will be reported to the Principal Investigator as soon as staff members are aware of them. If there is any doubt as to whether an event qualifies as a UE, AE, or SAE, staff members will be trained and encouraged to err on the side of caution – and to bring the event to the Principal Investigator's attention for review.

Attribution

The Principal Investigator, in consultation with the Co-Investigators, will decide if a UE should be classified as an AE. If an event is classified as an AE, further attribution will be determined, as follows:

- Related – AEs that are definitely, probably, or possibly related to the smoking cessation intervention.
- Not Related – AEs that are doubtfully related or clearly not related to the smoking cessation intervention.

Reporting

1. **SAE's:** For AE's meeting the criteria for an SAE, regardless of its attribution, a Fred Hutch SAE Report form will be completed. The SAE Report form will be faxed by the Principal Investigator to the IRO office at [contact] within 24 hours of the internal report. All available information will be submitted. Should additional information become available after the initial report, a revised report will be submitted within 15 days.
2. **AE's that do not meet the criteria for SAE:** For these events, the Principal Investigator or the Study Coordinator will complete and submit a Fred Hutch Adverse Event Reporting form within ten (10) calendar days of learning of the events.
3. **UE's that do not meet the criteria for AE's:** For these events, the Study Coordinator will complete and submit a Fred Hutch UE Reporting Form within ten (10) calendar days of learning of the events.

Complying with Trial Suspension Reporting Requirements

Were the Fred Hutch's IRB or Clinical Trial's Office to issue a temporary or permanent suspension of the trial, the trial's Principal Investigator will immediately contact the trial's project officer. A Data Safety Monitoring Board will not be required since this is a minimal risk behavioral intervention.

REFERENCES

1. U.S. Department of Health and Human Services. The Health Consequences of Smoking--50 Years of Progress: A Report of the Surgeon General. . In: US Department of Health and Human Services CfDCaP, National Center for Chronic Disease Prevention and Health Promotion, Office of Smoking and Health editor. Atlanta, GA2014.

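### The plan promises adverse-event monitoring, but no described survey content asks about serious events and no rule links the scheduled symptom scores to event review, so capture rests on unsolicited reports

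*Combined protocol and SAP*

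**What the plan says.** Under Guidelines for Monitoring and Reporting Unexpected and Adverse Events, the plan commits three study roles to surveillance: "Throughout the study, the Principal Investigator, Co-Investigator, and Project Manager will monitor participants for adverse events and protocol compliance". The definitions are broad: "Adverse events (AEs) are any untoward occurrence with a trial participant whether or not it can be considered to be related to their smoking cessation". Serious events include death, inpatient hospitalization and lasting disability.

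Two examples follow. For adverse events: "An example of an adverse event in this trial could include an increase in depressive symptoms". For serious ones: "In this trial, an example of a serious adverse event would be a suicide attempt". For every serious event, "regardless of its attribution, a Fred Hutch SAE Report form will be completed". Staff are to tell the principal investigator once they know of an event, and the reporting clocks run from that internal report or from learning of the event.

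Potential risks to participants accepts that "some participants might feel emotional upset during their assigned intervention".

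Follow-up data come from surveys at 3, 6 and 12 months. Follow-up survey methods gives the order of contact: first "Three email attempts to complete the online version of the survey", then up to eight telephone attempts, then a paper survey by post.

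**The concern.** Definitions, attribution categories and reporting deadlines are all present. The step before them is not: nothing says how staff come to know that an event happened. The trial is remote, with 2500 people planned and no clinic visits, and a participant who answers online need never speak to staff. The plan also dispenses with a data safety monitoring board, so the team's own event log is the main safety record described.

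If nobody is asked about hospital stays or suicide attempts, a short log has two explanations: few events, or few reports. The trial could not tell them apart, and the information could not be recovered afterwards.

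A second gap concerns the one type of event that is measured. Depressive symptoms are scored repeatedly, and a rise is the plan's own example of an adverse event, but no passage says whether or how a rise becomes a recorded event.

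**Working it through.** The plan states no figure to reproduce, so the main check sets its sections side by side.

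1. **Survey content.** Table 4 lists tobacco use, nicotine dependence, acceptance of cues, quality of life, mental-health symptom scales, alcohol use, receptivity and utilization, cessation aids and a few others. No row concerns adverse events, hospitalization or self-harm. The Survey Data section describes the 3-month survey as covering cessation processes, progress, outcomes and experience of the assigned app, and the later surveys as mainly cessation progress and outcomes.

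2. **Symptom scales.** The 20-item depression row carries four marks, as do panic, PTSD, generalized anxiety, social anxiety and alcohol use. Column alignment is damaged in the copy reviewed; I read the marks as baseline, 3, 6 and 12 months. Their stated purpose is the Exploratory Aim. No review step or link to event reporting is given.

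3. **Routes by which an event reaches staff.**
   - All participants may e-mail the principal investigator (Protection against emotional upset or embarrassment).
   - A toll-free number is mentioned in the voicemail text used during telephone follow-up.
   - A participant may mention an event during a telephone survey.

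   All three are unsolicited. Weekly e-mail reminders and the pre-survey letters are scheduled contacts, but they are not described as asking for anything about events.

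4. **People reached by surveys.** At the plan's 84% retention, 2500 × 0.84 = 2100 respond at a given follow-up and 2500 × 0.16 = 400 do not.

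5. **Illustration, on assumed inputs only.** Let s be the share of respondents who answer by telephone, and let p_T and p_O be the chances that an event is volunteered by telephone and otherwise. If non-responders report nothing:

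   share recorded = 0.84 × [s × p_T + (1 − s) × p_O]

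   - Low end (s = 0.10, p_T = 0.30, p_O = 0.05): 0.84 × (0.030 + 0.045) = 0.063.
   - High end (s = 0.50, p_T = 0.50, p_O = 0.10): 0.84 × (0.25 + 0.05) = 0.252.

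   With an assumed true serious-event risk of 2%, 2500 × 0.02 = 50 events, of which about 3 to 13 would be recorded. None of s, p_T, p_O or the risk is in the documents. The range shows what unsolicited capture could look like; it does not forecast it.

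**The case against.** Several points on the other side stand.

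- **The surveys do touch on adverse events.** A reader might infer that they ask about none. That goes too far: depression, anxiety, PTSD, panic and alcohol measures are scheduled at follow-up in both arms. What remains is that no rule turns those scores into event review, and that none of these rows is described as covering a hospital stay or a suicide attempt.
- **The serious-event rule can be met.** A reader might infer that it is unworkable. It is not: the duty starts when staff become aware, so staff can comply fully with an incomplete log. The promise of monitoring is what lacks a method.
- **An app-upset question may already exist.** Table 4 gives block names and item counts, not wording. The 3-month receptivity block has 14 items and could include one.
- **Bias between arms is not shown.** Live contact is described only at the telephone step, so counts may vary by mode. A reader might go on to infer a spurious difference between arms. That needs online response to differ by arm, although a blinded unit applies the same sequence to both. For example, assume 5% true risk in 1250 per arm, volunteering of 5% online and 30% by telephone, and online shares of 70% and 60%. Recorded events are then 62.5 × 0.125 = 7.8 and 62.5 × 0.150 = 9.4, a ratio of 1.20. Every input is assumed, and the gap of 1.6 is well within a Poisson standard error of √(7.8 + 9.4) ≈ 4.1.
- **Risk is described as minimal, and no aim compares events by arm.** This limits the consequence. It does not supply the method that the monitoring promise needs, and the plan itself names emotional upset as a risk.

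**Conclusion.** The concern holds in a limited form. The plan promises monitoring throughout, but describes no question that would detect the serious events it defines and no link from the scheduled symptom scores to event review. Serious-event capture therefore depends on unsolicited contact, will probably be incomplete, and may vary by survey mode. A low count could not support a statement that either app is safe.

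The size of the shortfall cannot be derived from the documents, and the conclusion does not rest on the illustration. It rests on Table 4 and the survey descriptions being a complete account of survey content. If the full questionnaires already contain a serious-event item, that part of the point falls away. The efficacy analyses are not affected.

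**What to change.** 1. Add one closed item to the 3-, 6- and 12-month surveys asking whether any event meeting the plan's own serious-event criteria has occurred since the last survey (since enrolment, at 3 months). Use identical wording in both arms and in the online, telephone and mailed versions.
2. Check the receptivity block. If it does not ask about upset from the assigned app, add one such item.
3. Report both items by arm, with the number of respondents as the denominator. List spontaneous reports separately.
4. Tabulate the symptom scores already being collected by arm at each follow-up. The sponsor should reconcile those scores with the adverse-event definition and state whether, and how, they feed event review.

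**Cost.** One or two closed items per survey and a short table. More events will be found, and because reporting duties start at awareness, more serious and non-serious event forms will follow. The sponsor will also need a procedure for positive answers given online, where no staff member is present.

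**Limits.** The items will not capture deaths or events among the roughly 16% expected not to respond. Events may come to light months late, up to about six months between the last two surveys.
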